## 12. Risk Mitigation

A project-specific risk assessment has been performed and is documented below as per Standard Operating Procedure (UoB SOP PROJECT OVERSIGHT & QUALITY MANAGEMENT: UoB-POS-SOP-001, V3.0, 8.1.2024).

- Risk: Potential for insufficient recruitment from the community
   Mitigation: We have allowed additional time (3 months) for recruitment in our study plan to allow for
   slower recruitment in some months (estimated 1-2 participants per months after data collection
   starts). We are also co-producing recruitment materials with specifically recruited Birmingham YAG
   members to ensure that our participant-facing materials are as inclusive as possible and are attractive
   to the community.
- Risk: It is possible that some participants may find it difficult to understand instructions regarding study processes.
   Mitigation: We will give these both verbally and in written form, and will check understanding prior to study procedures.
- 3. Risk: It is possible that participants may have varying sub-clinical cognitive and mood differences at recruitment, which may impair our ability to detect signal in neurocognitive measures.

UOB ethics number: ERN 3117

Mitigation: We will assess baseline mood and subjective cognitive difficulties, and we can incorporate these into analytical models as necessary to account for subclinical differences in cognition and mood.

[figure not shown]
- 4. Risk: Participants may deteriorate in terms of mental state during the course of the study. Mitigation: As the study is short, and involves only healthy volunteers, this is unlikely to occur. However, we will monitor the results of the SCID at screening, and the PHQ-9, GAD-7 and PLE during each study visit. Any concerns will be discussed with the PI and / or supervising medical investigators, all of whom are psychiatrists with experience in managing patients with serious mental illness and suicidal thoughts and behaviours. We will also ask all participants to provide the details of a GP or other health professional so that the study team can advise them of their participation in the study
- 5. Risk: Bias from accidental unblinding Mitigation: To preserve the blind, prucalopride and placebo will be encapsulated to appear identical and labelled blinded. The randomisation list will be generated by an independent pharmacist and access to the unblinded code list will be restricted to the randomisation service provider.
- 6. Risk: Participant becomes pregnant during the study Mitigation: Given the short duration of the medication course and the requirement for a negative pregnancy test at screening, the likelihood of a pregnancy occurring during this study is very low. However, participants will be advised to avoid becoming pregnant during this time. This is because, although there are no known risks of prucalopride in pregnancy, it is not currently recommended during pregnancy. If a participant does become pregnant, they will be instructed to inform a member of the research team and consult their healthcare provider or General Practitioner for further guidance and to stop taking the medication if the study is still in progress.

A health and safety risk assessment and a biological risk assessment will be completed prior to commencement of the study, and updated during the study where necessary as per the SOP above.

## 13. Public Involvement (PPIE)

We will involve lived experience advisors throughout the research as per standard practice for the Institute for Mental Health, UoB and the Standard Operating Procedure PARTICIPANT ENGAGEMENT AND INFORMED CONSENT (UoB-PEI-SOP-001). The University of Birmingham Institute for Mental Health's PPI Youth Advisory Group (IMH YAG) provided detailed in-person feedback on the study proposal when it was presented at their 20th February 2024 meeting. This directly fed into funding proposals and the protocol including the amount of remuneration to offer participants, and we were able to confirm with them that in their opinion participants would be happy to undertake minimally invasive blood tests and would like to be offered daily SMS text reminders to take their study medication.

Similar to other studies, the Institute for Mental Health PPIE lead ([name]) and his team are supporting us to recruit three individuals from the YAG to co-produce this project via a study-specific lived experience advisory group (LEAG). They will be reimbursed for their time to participate in discussion groups (meetings every 3 months to provide ongoing PPIE feedback and oversight), read research documentation (such as the participant information sheet (PIS)) and provide comments, and be involved in wider publicity and dissemination of research findings. Costs also include travel for face-to-face consultation where this is required. Based on previous experimental trials and NIHR-guidance, this is costed at £25/hour per person.

UOB ethics number: ERN\_3117

### 14. Ethical Considerations

#### 14.1 Ethical approval

Prior to the commencement of the study, the protocol and any subsequent amendment(s), Participant Information and Consent Form, other information provided to participants (including advertising) and product information, will be submitted for NHS ethical approval via IRAS (Integrated Research Application System). The approval letter should refer to the study by title, protocol number and version and dates of documentation reviewed and approved. A copy of the signed and dated letter of approval (on institutional letterhead) will be provided before study commencement.

During the course of the study, the Principal Investigator / Sponsor is required to submit the following to the ethics committee: any amendments to the protocol; progress reports according to regulations and guidelines; Final Study Report as required.

Protocol amendments will be agreed upon by the PI, supervising medical investigator, and the Sponsor and submitted to the ethics committee for approval prior to implementation.

#### 14.2 Ethical practice during study

The Investigator will ensure that the study is performed in accordance with ethical principles that have their origin in the Declaration of Helsinki and are consistent with International Conference on Harmonisation (ICH) Good Clinical Practice (GCP).

#### 14.3 Informed consent procedure

Prior to participation in the research study, each participant will undergo a complete consenting interview with the delegated study team members and provide consent on the ethically-approved form. The contents and process of obtaining informed consent will be in accordance with all applicable regulatory requirements. All delegated study team members taking part in informed consent will have appropriate training.

All eligible participants will have the study explained by the PI or the delegated assistant / other study member. They will receive a full explanation, in lay terms of the aims of the study, the discomfort, risks and benefits in taking part as well as insurance and other procedures for compensation in case of injury. It will be explained that the study is for research purposes and may not provide benefit to the individual. It will be pointed out that they can withdraw from the study at any time without prejudice. Each participant will acknowledge receipt of this information by giving informed consent for participation in the study. Informed consent may also be provided electronically. The participant will be given a copy of the signed or electronically acknowledged Participant Informed Consent Form (ICF) to retain. All study documents will be fully approved by the ethics committee prior to being used for consenting purposes. The Joint statement on seeking consent by electronic methods (PDF - 209 KB) advice issued by the HRA and MHRA will be followed when consent is taken electronically (see 14.3 Informed Consent).

#### 14.4 Participant data protection

The ICF will explain that study data will be safely stored in computer databases. Participants in this database are identified by a unique participant identification number and their initials. Adherence to the Data Protection Act and General Data Protection Regulation Act 2018 is applicable.

UNIVERSITYOF BIRMINGHAM

V2, Date 03/09/25 Short title: SERENE UOB ethics number: ERN\_3117

## 15. Study Management & Monitoring

#### 15.1 Study Oversight

A formal Data Safety and Monitoring Committee will not be established due to the size of the project and the low-risk nature of the intervention (use of a licensed drug in medically healthy individuals, where previous studies [13] have demonstrated excellent tolerability).

Safety signals (adverse events) will be regularly reviewed by the PI and other medically trained personnel, and discussed with other investigators during Study Management Group meetings (occurring 3-4 monthly during the study), and the Sponsor if required, as per the Standard Operating Procedure (UoB SOP: ADVERSE EVENT REPORTING, V2.0, 20.1.2023).

The Study Management Group will consist of the PI, the Supervising and Co-Supervising Medical Leads, the Laboratory Lead, and any Study-specific Research Assistants and Lived Experience Consultants.

#### 15.2 Monitoring and auditing

Study monitoring will be performed in accordance with applicable regulations, ICH-GCP, and University of Birmingham Standard Operating Procedures (SOPs). An audit is a systematic and independent examination of study-related activities and documents to determine whether the approved study-related activities were conducted, and the data were recorded, analysed and accurately reported according to the protocol, SOPs and any applicable institutional requirements.

The Investigators will ensure that direct access to source data / documents for the purposes of monitoring, audits, ethics review and regulatory inspections is available throughout the study and during the record retention period. In addition, the PI will ensure that each study participant has consented, in writing, to their records being available for monitoring audits and regulatory inspections.

Considering the small sample size over a single site, it will be appropriate to monitor the study as follows: At each three-four monthly Study Management Group meetings the following aspects of the study will be reviewed and minuted.

[figure not shown]
- Numbers and completeness of case report form (eCRF)
- Compliance with the protocol's treatment according to participant report
- Any adverse event report form completed
- Any notification of protocol deviations
- Any concerns regarding quality of data

#### 15.3 Staff training

As per GCP, each individual involved in the conduct of a study will be qualified by education, training and experience to perform his or her respective tasks. The PI will maintain a record of all individuals involved in the study. The PI will ensure that appropriate training relevant to the study is given to staff, and that they will receive any new information of relevance to the performance of this study.

#### 15.4 Study amendments

Study procedures will not be changed without the mutual agreement of the PI, the Sponsor and ethics committee. If it is necessary for the study protocol to be amended, the amendment or a new version of the study protocol must be approved by the ethics committee. If a deviation or change to a protocol is implemented to eliminate an immediate hazard(s) prior to obtaining ethical approval, the deviation or change will be submitted to the ethics committee for review and approval.

15.5 Study completion

The end of the study will be the date of the final study visit for the final participant.

## Data Management

#### 16.1 Sample size calculation

Previous studies investigating the effect of prucalopride / other serotonergic drugs on acute cognition assessed with behavioural measures indicate an effect size of 0.8-0.9 may be expected. As relatively little is known about 5-HT4R stimulation in healthy participants we PLEs, we conservatively estimated a smaller effect size (0.5-0.7) for sample size calculation. This indicates 15-17 participants/group would give 85-90% power to detect a significant group difference at a 0.05 false positive rate. We aim to recruit up to 36 (18 in each group) to allow for withdrawals and exclusions for data quality reasons.

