#### 7.2 Sample size

The study will be complete when there is full data for 36 participants meeting inclusion criteria.

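### The 85-90% power in Protocol section 16.1 cannot be reproduced from its own inputs; read as Cohen's d without baseline adjustment, it is about 26-51%

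*Protocol*

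**What the plan says.** Section 16.1 reports that earlier studies of prucalopride and other serotonergic drugs "indicate an effect size of 0.8-0.9 may be expected". Because little is known in this population, the authors then write that "we conservatively estimated a smaller effect size (0.5-0.7) for sample size calculation". The result is: "This indicates 15-17 participants/group would give 85-90% power to detect a significant group difference at a 0.05 false positive rate". On recruitment, the section adds: "We aim to recruit up to 36 (18 in each group) to allow for withdrawals and exclusions for data quality reasons". Section 7.2 puts completion differently: "The study will be complete when there is full data for 36 participants meeting inclusion criteria". Figures are therefore given below for 18 per group as well as 15-17.

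Section 16.1 does not say which effect-size metric is meant, whether the test is one- or two-sided, which test or task is powered, or whether a baseline to follow-up correlation was assumed. The design is two parallel groups, 1:1 (section 3). Section 17.1 plans ANCOVA or linear mixed models on baseline and follow-up for the behavioural tasks other than the FERT. For the FERT it plans a repeated-measures ANOVA with group and emotion as factors.

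**The concern.** In a two-group comparison, lowering the assumed effect from 0.8-0.9 to 0.5-0.7 should raise the required sample sharply. Here the discounted effect leads to 15-17 per group, which would be small even for the larger effect.

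The figure matters because it is the protocol's justification for N = 36, and because section 5.3 says the study should supply proof of principle and an effect size for later trials. An ethics committee or a later trial designer who relies on 85-90% would think the study far better able to detect 0.5-0.7 than the stated inputs show. They would also give a non-significant result more weight than it can bear.

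**Working it through.** **Inputs from section 16.1.** Alpha 0.05; effect 0.5-0.7 (earlier studies 0.8-0.9); n = 15-17 per group, with 18 recruited; stated power 85-90%. **Assumed, because not stated:** effect size is Cohen's d (between-group difference divided by SD), two-sided test.

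**Step 1: attempt to reproduce the stated figure.** For a two-sample t-test with n per group, the noncentrality is d × √(n/2) on 2n − 2 degrees of freedom. Power is the chance that |t| exceeds its critical value (2.048 at n = 15, 2.037 at n = 17, 2.032 at n = 18).

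- d = 0.5, n = 15: 0.5 × √7.5 = 1.37, power 26.2%.
- d = 0.7, n = 17: 0.7 × √8.5 = 2.04, power 50.8%.

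| d | n = 15 | n = 17 | n = 18 |
|---|---|---|---|
| 0.5 | 26.2% | 29.3% | 30.8% |
| 0.7 | 45.7% | 50.8% | 53.2% |
| 0.8 | 56.2% | 61.9% | 64.5% |
| 0.9 | 66.3% | 72.1% | 74.6% |

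The stated 85-90% appears nowhere in the table. A one-sided 0.05 test at d = 0.5-0.7 and n = 15-17 gives 38-64%, which is also short.

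**Step 2: solve in the other direction.**

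- The d that gives 85% / 90% power is 1.13 / 1.23 at n = 15 and 1.06 / 1.15 at n = 17. All exceed the 0.8-0.9 quoted from earlier studies.
- The n per group for 85% / 90% power is 73 / 86 at d = 0.5 and 38 / 44 at d = 0.7.
- The d detectable with 80% power is about 1.06 at n = 15 and 0.99 at n = 17.

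**Step 3: allow for the ANCOVA option in section 17.1.** Adjusting for a baseline with correlation r to follow-up gives an effective d of d/√(1 − r²). For d = 0.5 and r = 0.9 this is 0.5/√0.19 = 1.147. Values of r are assumptions; the protocol gives none.

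| Assumed r | Lowest power (d = 0.5, n = 15) | Highest power (d = 0.7, n = 17) |
|---|---|---|
| 0.5 | 33% | 63% |
| 0.7 | 46% | 79% |
| 0.8 | 60% | 91% |
| 0.9 | 86% | 99% |

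Solving r = √(1 − (d/d_eff)²) with the effective d from step 2, 85-90% power needs r of about 0.88-0.91 at d = 0.5 and about 0.75-0.82 at d = 0.7.

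**Step 4: try Cohen's f.** For two groups d = 2f, so f = 0.5-0.7 means d = 1.0-1.4. Power at n = 15-17 then runs from 75% to 98%, and 85-90% falls only mid-range. A group-by-time interaction f of 0.25-0.35 with r = 0.5 gives the same 75-98% and corresponds to a difference in change of 1.0-1.4 SD.

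**Step 5: what a significant result would look like.** Unadjusted, the observed difference must exceed about 2.037 × √(2/17) = 0.70 SD at 17 per group, or 2.032 × √(2/18) = 0.68 SD at 18 per group. If the true effect lies in 0.5-0.7, selecting on significance pushes the reported estimate upwards on average.

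**The case against.** The strongest reply is that the unadjusted t-test is not what section 17.1 plans for most tasks. Baseline adjustment raises power, and with a high enough correlation the claim can be met. This stands to the extent that 26-51% cannot be called the power of the design: that power is undetermined until a correlation is stated. It does not rescue the sentence, because the whole 0.5-0.7 range reaches 85-90% only near r = 0.9, an assumption found nowhere in the protocol. The FERT outline in section 17.1 also names only group and emotion, with no baseline term.

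A second reply is that the metric is unstated and may be Cohen's f. That is possible, but section 16.1 sets 0.5-0.7 against 0.8-0.9 as a smaller value of the same kind. If only the 0.5-0.7 is an f, it equals a d of 1.0-1.4 and is larger than the 0.8-0.9 it is meant to discount. If both are f, the earlier effects would be 1.6-1.8 SD (2 × 0.8 to 2 × 0.9), and the section should say so.

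A reader might also infer stronger points that the protocol does not support:

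- **That a null result will be over-read.** The protocol does not say how a null result will be interpreted.
- **That the study will miss a true effect more often than it finds one, across the whole range.** At d = 0.7 unadjusted power is 51-53% with 17-18 per group.
- **That every significant estimate will be too large.** The 0.68 SD threshold at 18 per group lies below 0.7, so the exaggeration holds on average only.
- **That totals were confused with per-group numbers.** At d = 0.8 the requirement is 30 and 34 per group for 85% and 90%, which equals the totals implied by 15-17 per group. The match is suggestive but proves nothing.

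**Conclusion.** The point holds as a failure to reproduce. The 85-90% does not follow from 0.5-0.7, 15-17 per group and alpha 0.05. With d, a two-sided test and no adjustment, the gap is large: 26-51% against 85-90%. The claim also fails at the undiscounted 0.8-0.9 (56-72%). With ANCOVA the size of the gap depends on an unstated correlation.

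The practical consequence is limited but real: a non-significant result would be weak evidence against 0.5-0.7, and a significant one would on average overstate the effect passed to the next trial. The exact percentages rest on reading the effect as Cohen's d and on a two-sided 0.05 test. The conclusion that the sentence needs correcting holds under the other readings tried, since each needs an input or metric that section 16.1 does not give.

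**What to change.** In section 16.1, first state the effect metric, sidedness, test, endpoint and any assumed baseline to follow-up correlation. Then restate the power or detectable difference that follows from them.

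If the metric is d, with a two-sided 0.05 test and no adjustment, the replacement could read: with 15 evaluable participants per group the study has 80% power for a standardised difference of about 1.06, and with 17 per group about 0.99; power for 0.5-0.7 is about 26-51%. Any ANCOVA figure should be shown over a labelled range of assumed correlations, such as 33-63% at r = 0.5 and 46-79% at r = 0.7. Remove the word *conservatively* unless the restated metric supports it.

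The cost is one paragraph of protocol wording and a less favourable stated power. No extra participants are needed for this correction.

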#### 16.2 Trial master file

All essential documents relating to the study will be kept in the Trial Master File (TMF) as per the UoB Essential Documents Checklist (UoB-ESD-QCD-001). This will be maintained and stored securely during the study. The TMF will be archived appropriately as below (see 15.3.6 Data Archiving).

#### 16.3 Data management plan

Data management will be conducted in line with UoB Standard Operating Procedures (UoB SOP: DATA MANAGEMENT, V1.0, 3.1.2023 (UoB-DMA-SOP-001), adhering to the UoB Principles of GCP for Clinical Research (UoB-GCP-POL-001). All investigators and site staff must comply with the requirements of the Data Protection Act 2018 with regards to the collection, storage, processing and disclosure of personal information and will uphold the Act's core principles.

#### 16.3.1 Data collection methods

Data collected will consist of:

- Demographic, medical and psychiatric interview and physical observations data (collected and stored electronically using an electronic case report form (eCRF))
- Questionnaire data (collected and stored electronically)
- Neurocognitive task data (collected and stored electronically)
- MRI scan data (collected and stored using MRI secure servers) and contemporaneous physiological measurement data (collected and stored electronically)
- Blood samples. These will be collected, handled, and transported securely for pre-processing, storage of acellular material, and analysis under [name] team at the University of Birmingham (data from analysis will be stored electronically). Storage of Peripheral Blood Mononuclear Cells (PBMCs) will be via the HBRC for at least 5 years.
- Microbiome samples. Samples will be collected at participants homes and either transported by post or via study researchers to [name] Laboratory group, based in the Institute of Microbiology and Infection at the University of Birmingham.

Consent forms (ICF) will be stored electronically with participants receiving a paper copy for their own records.

UOB ethics number: ERN 3117

The eCRF will be created according to UoB Standard Operating Procedures (UoB SOP: CASE REPORT FORM DEVELOPMENT (UoB-CRT-CRF-SOP-001).

Coding and analysis of data will be documented in advance using the Statistical Analysis Plan.

#### 16.3.2 Participant log and link key

A screening log of all potential participants will be maintained. This will include potential participants who were considered but later deemed ineligible due to meeting one of the exclusion criteria or withdrew. The reasons for exclusion or refusal will also be recorded against their ineligibility / refusal status. This log will be stored securely on University of Birmingham servers. For participants who withdraw up to the end of data analysis, their data will be withdrawn. It will not be possible to withdraw data, once data analysis has completed. This will be communicated in the PIS.

All participants who are considered for or enrolled in the study will receive an individual identification number (Participant ID). Documentation regarding potential participants and participants enrolled in the study will only be accessible to study team members who need this information for conducting the study. All data collection will use the Participant ID to link the data to one individual. The key that links Participant ID and participant names will be stored on secure University of Birmingham servers and will be kept until publication of the study.

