#### 7.6 Withdrawal

Participants are free to withdraw at any time up to the end of data analysis, without affecting their clinical care or association with the University, and do not need to give a reason for this to the investigators.

Rarely, it may be necessary for participants to withdraw from the study if they feel unwell or there is a concern from one of the study team. If this happens, the PI will discuss with the participant the reasons for withdrawal and any future plans to ensure that the participant's wellbeing is maintained.

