#### 7.7 Replacement of Participants

Participants who discontinued from the study may be replaced.

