#### 17. Statistical Methods

Data analysis will be outlined in the Statistical Analysis Plan (SAP), which will be approved by the study team and uploaded to clinicaltrials.gov prior to analysis. The CI (or their delegate) will lock the data from any further changes once data collection has been completed and the SAP approved to allow for statistical analyses to begin (as per the UoB SOP: Statistics (UoB-STA-SOP-001)).

An outline of planned analysis is given below.

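### By default, all data of anyone who withdraws before analysis ends are removed; this conflicts with the data lock, is not reconciled with adverse event reporting, and lets the analysed set be selected after randomisation

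*Protocol*

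**What the plan says.** The rule is in Protocol section 16.3.2: "For participants who withdraw up to the end of data analysis, their data will be withdrawn". The next sentence sets its only limit: "It will not be possible to withdraw data, once data analysis has completed". The section adds that participants will be told this in the PIS.

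Other sections bear on who is affected and when:

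- **7.6 Withdrawal.** Participants may leave without giving a reason until analysis ends. In addition, "Rarely, it may be necessary for participants to withdraw from the study if they feel unwell or there is a concern" on the part of the study team.
- **7.7 Replacement of Participants.** "Participants who discontinued from the study may be replaced".
- **7.2 Sample size.** "The study will be complete when there is full data for 36 participants meeting inclusion criteria".
- **16.1 Sample size calculation.** "We aim to recruit up to 36 (18 in each group) to allow for withdrawals and exclusions for data quality reasons".
- **17 Statistical Methods.** The chief investigator or a delegate "will lock the data from any further changes once data collection has been completed and the SAP approved", so that analysis can start.
- **11 Safety Measures.** Adverse events are recorded, investigated and reported under an SOP. The side effects checklist is completed at baseline and at study end, and section 17.1 compares it between groups over those two time points.

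**The concern.** Removal follows automatically from withdrawing. It is not something the participant has to request. Because withdrawal includes leaving when unwell or at the team's concern, the people removed may differ from those who stay in ways related to treatment. Replacement and a completion rule based on full data then fill the places with people who stayed. The comparison can therefore move from everyone randomised to a group selected after randomisation.

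This matters more than usual here because section 5.3 gives an effect size estimate for later trials as one purpose of the study. A statistical analysis plan can choose an analysis set, but it cannot bring back data already withdrawn. Since the rule goes into the PIS, it also becomes an undertaking to each participant who enrols.

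**Working it through.** **1. Order of events.** Under section 17 the sequence is: data collection ends, the SAP is approved, the data are locked, analysis begins, analysis ends. Section 16.3.2 requires removal for any withdrawal up to the last of these. Between lock and the end of analysis, one section forbids changes and the other requires them. This contradiction needs no assumption about dropout.

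**2. What the rule itself takes away.** There is one follow-up visit, so the cases separate cleanly.

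| Participant | Under 16.3.2 | If data up to withdrawal were kept |
|---|---|---|
| Withdraws before Visit 3 | Baseline data removed; status of adverse event records not stated | Baseline and adverse event data kept; still no follow-up outcome |
| Completes Visit 3, withdraws before analysis ends | Both visits removed, even after lock | Both visits kept unless removal is requested before lock |
| Stops capsules, attends Visit 3 | Not said to count as withdrawal | Both visits kept |
| Misses Visit 3 without withdrawing | Not covered by the rule | Baseline kept |

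The rule changes the efficacy data mainly in the second row. In the first row the outcome is missing either way.

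**3. Safety data.** An early withdrawer has no study-end checklist, and the baseline one is removed. A late withdrawer loses both. Adverse events run on a separate track (sections 11, 15.1 and 15.2), but no section says whether those records are exempt from 16.3.2.

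**4. The protocol's own allowance.** Section 16.1 recruits 18 per group against 15-17 needed:

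- (18 − 17)/18 = 1/18 = 5.6%
- (18 − 15)/18 = 3/18 = 16.7%

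That is 1-3 losses per arm, covering withdrawals and data-quality exclusions together. The 15-17 is taken as stated. A plain two-sided two-sample comparison at effect sizes 0.5-0.7 would need 37-85 per group for 85-90% power, but that is a separate matter. The allowance also does not fit section 7.2: a total of 36 recruited cannot both absorb losses and yield full data for 36.

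**5. Possible shift in an arm mean.** If a share p of one arm is removed, and those retained score D standard deviations better on average than those removed, the retained mean exceeds the full-arm mean by p × D. The protocol gives no D; 0 to 1.0 SD is an assumption.

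| D (SD) | 1 of 18 removed | 3 of 18 removed |
|---|---|---|
| 0 | 0 | 0 |
| 0.5 | 0.056 × 0.5 = 0.03 | 0.167 × 0.5 = 0.08 |
| 1.0 | 0.056 × 1.0 = 0.06 | 0.167 × 1.0 = 0.17 |

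The planning effect is 0.5-0.7. As an extreme, a simulation of 18 per arm with no true effect, in which the lowest scorers of one arm are the ones removed, gives 0.11, 0.20 and 0.28 SD for 1, 2 and 3 removed. If similar people leave both arms, the shifts cancel; if those who leave would have scored better, the sign reverses. For people without Visit 3, whatever shift arises would be there under either rule. Only removal of completed records makes it a cost of section 16.3.2.

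**6. Replacement.** Bottles are issued in numerical order from a blocked list stratified by gender (section 9). A replacement takes the next code, which is a fresh random allocation and need not restore the arm that lost someone.

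**The case against.** The strongest reply is that the rule does little harm of its own. With two assessment points, a person who leaves early contributes no on-treatment outcome whether or not the baseline record is kept, and a baseline record alone adds almost nothing to the treatment contrast. Withdrawal for illness is described as rare, dosing lasts 7-10 days, and side effects at a check-in lead to a clinician's discussion, not automatic withdrawal. This stands, and it is why no particular bias can be claimed.

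Four stronger readings are tempting, and the documents do not support them:

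- **That the analysis is completers-only.** No analysis set is named, analysis is left to the SAP, and people who stop capsules or miss Visit 3 without withdrawing fall outside the rule.
- **That drug-related dropouts disappear from the tolerability results.** Adverse events are recorded under an SOP and reviewed at management meetings, and the screening log includes people who withdrew. Nothing says these records are erased. The fault is that nothing says they are exempt.
- **That the people removed are necessarily selected by treatment.** Section 7.6 also allows withdrawal for any reason or none. Selection by treatment is possible, not established.
- **That the records are destroyed.** The text says data are withdrawn. For the analysis the effect is the same, but erasure is not stated.

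It may also be said that leaving out a person's record is different from editing locked values. That softens the lock conflict but does not remove it: the set analysed can still change after lock.

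**Conclusion.** The concern holds as a defect in a stated rule. Three parts rest on the text alone: removal is the default with no exception for data already collected or for adverse event records; it can continue after the lock in section 17; and it is not reconciled with section 11. Together with sections 7.2, 7.6 and 7.7, it allows the analysed set to be selected after randomisation.

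The size is open. Using the 1-3 losses per arm that section 16.1 allows for, all in one arm, and an assumed difference of 0 to 1.0 SD, the shift in that arm's mean is 0 to 0.17 SD. Zero is a real possibility, and the part due to missing Visit 3 data would remain whatever the rule. The case for change rests on irreversibility and on the conflicts between sections, not on a predicted bias.

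**What to change.** Amend sections 16.3.2 and 7.6 and the PIS as follows:

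1. Data collected up to withdrawal are kept and analysed by default. They are removed only on the participant's explicit request, and only until data lock.
2. Adverse event records and withdrawal counts are retained, and are reported by arm for everyone who took study medication.
3. Three events are kept apart: stopping study medication (still invited to Visit 3), leaving the study, and withdrawing consent to data use.
4. Any participant who is replaced under section 7.7 stays in the randomised set.
5. Sections 7.2, 7.6, 7.7, 11, 16.3.2 and 17 are reconciled with each other, and section 7.2 with the recruitment ceiling in section 16.1.

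The cost is one protocol and PIS amendment with ethics committee approval. No extra participants or new procedures are needed. It is best made before or early in recruitment, because each participant who enrols is told the present rule.
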